3 ABBREVIATIONS

3T MR	3 Tesla magnetic resonance imaging
AE	Adverse Event/Incident – unwanted medical event
AES	The Apathy Evaluation Scale
BOLD	Blood-oxygen-level dependent imaging
CRF	Case Report Form
CRP	C-reactive Protein
D3 receptor	D3 dopamine receptor
DARS	Dimensional Anhedonia Rating Scale
DSF	European Union General Data Protection Regulation (EU 2016/679) (GDPR)
DSM-5	Diagnostic and Statistical Manual of Mental Disorders 5 ed.
eCRF	Electronic Case Report Form
ECT	Electroconvulsive therapy
eGFR	Estimated glomerular filtration rate
EU	European Union
Eu CTR	EU Clinical Trials Register
FASS	Pharmaceutical Specialties in Sweden
fMRI	Functional magnetic resonance imaging
GAD-7	Generalized Anxiety Disorder-7
GCP	Good Clinical Practice
Hb	Hemoglobin
ICD-10	International Statistical Classification of Diseases and Related Health Problems 10 ed.
ICH	International Council for Harmonisation
ICMJE	International Committee of Medical Journal Editors
IL	Interleukin
Source data	Any information in original and certified copies of original documents of clinical findings, observations, or other activities in a clinical trial necessary for the reconstruction and evaluation of the study. The source data is contained in source documents (original or certified copies). (ICH-GCP E6)

LPT	The Act on Compulsory Psychiatric Care
LV	Swedish Medical Products Agency
LVFS 2011:19	Guidance to the Medical Products Agency's regulations on clinical trials of medicinal products in humans
MADRS	Montgomery-Åsberg Depression Rating Scale
MAOIs	Monoamine oxidase inhibitors
MAP-SR	Motivation and Pleasure Scale – Self-Report
MID-task	Monetary Incentive Delay task
MINI	Mini International Neuropsychiatric Interview
Monitor	An independent person who reviews that the study is conducted, documented, and reported in accordance with approved study protocols, Standard Operating Procedures (SOPs), Good Clinical Practice (GCP), and applicable regulatory requirements.
NAc	Nucleus accumbens
PAL	Patient-responsible doctor at a psychiatric ward or health center
PoC	Proof-of-Concept
Investigator	A licensed physician or licensed dentist performing trial at a trial site
PS	Parkinson's disease
EPM	The Ethical Review Authority
RCT	Randomized controlled trial
SAE	Serious Adverse Event – serious unwanted medical event
SD	Standard Deviation
SHAPS	Snaith–Hamilton Pleasure Scale
SmPC	Summary of Product Characteristics - a document written by the manufacturer at the time of registration of a medicinal product and is a summary of the characteristics and use of the medicinal product.
SSRI	Selective serotonin reuptake inhibitors
SUAS	Suicide Assessment Scale
SUS	Skåne University Hospital
SUSAR	Suspected Unexpected Serious Adverse Reaction
TNF	Tumor Necrosis Factor
YMRS	Young Mania Rating Scale

5 SYNOPSIS

Sponsors Protocol ID	1.1 20190619
Title	Adjunctive treatment with Pramipexole for Anhedonia Symptoms in Depression – A Pilot Study
EudraCT nr.	2019-001907-19
Background and expected benefits	The majority of depressed patients do not achieve remission with current treatment methods. Many continue to suffer from severe residual symptoms of anhedonia – the inability to experience pleasure and a reduced sense of drive – after treatment. At present, there is no specific and effective treatment available for anhedonia. Pramipexole, a dopamine agonist used in Parkinson's disease, has been shown to be effective against anhedonic symptoms in that condition. Clinical experience has also demonstrated treatment effects of high-dose pramipexole in treatment-resistant depression; however, randomized clinical trials have only been conducted with low-dose pramipexole and have not specifically examined its effects on anhedonia. This pilot study is expected to serve as a basis for a larger placebo-controlled randomized treatment trial of high-dose pramipexole as an adjunctive therapy in depression with severe anhedonic symptoms.
Objective	
Primary question: Do anhedonia symptoms, as assessed by the Dimensional Anhedonia Ration Scale (DARS) self-assessment questionnaire, decrease after 10 weeks of additional treatment with pramipexole?
 
Secondary/Exploratory questions:
 
 1. Does adjuvant treatment with pramipexole lead to improvement in General Depression symptoms, anxiety symptoms, sleep, apathy and fatigue? 2. Does adjunctive treatment with pramipexole lead to increased activity in the brain's reward system? Is such a change linked to clinical efficacy? 3. Is high-dose treatment with pramipexole a tolerable treatment in terms of side effects?
Variables	
Primary Variable(s): Total score DARS.
 
Secondary variable/variables: Total score Montgomery-Åsberg Depression Rating Scale (MADRS), BOLD signal at MID-task (fMRI), rating scales related to sleep problems, apathy, fatigue and anxiety. AE (Adverse Medical Event).

Investigational drug/treatment	Pramipexole prolonged-release tablet, 0.375 mg to 4.5 mg salt/day for 10 weeks (individually varying dose based on efficacy and side effects titrated during these weeks)

Study population	
Inclusion (not exhaustive list): Age between 18 years and 75 years Diagnosis of unipolar depressive episode, bipolar disorder in depressive phase or dysthymia. Moderate to severe depression but with pronounced symptoms of anhedonia. To be able to participate, you must have an ongoing stable treatment with at least an antidepressant/mood stabilizer for at least 4 weeks.
 
Exclusion (not exhaustive list): Current pregnancy, breastfeeding or planned pregnancy. High suicidal. Substance abuse. Psychotic disorder. Compulsory treatment (LPT). Impulse control disorder. Diagnosis of moderate/severe renal failure or severe cardiovascular disease. Recently started psychotherapy. Ongoing ECT treatment.

Study design	
Proof of concept study, in which fifteen research subjects are included and receive study treatment (no placebo or control group occurs). All included research subjects will also be asked to participate in the substudy for fMRI examination before and after 10 weeks of treatment with pramipexole.

Timetable	
Study start: 1 September 2019 Study end: 1 December 2020.

Statistical considerations	
The objective of the study is to demonstrate feasibility (proof of concept) and we hope to generate preliminary data that will form the basis for a larger, definitive, randomized controlled trial. Specifically, we are interested in investigating: i) can we pick up a signal in our material that pramipexole has an anti-anhedonic effect in this study population, (ii) if the treatment doses we propose are reasonable: treatment effect versus side effects, iii) what the distribution looks like for DARS before and after treatment in order to optimize future dimension calculations.

Method description	
Patients will be recruited from outpatient psychiatric clinics or inpatient wards. Those who meet the inclusion criteria and none of the exclusion criteria will, at the screening visit, undergo a baseline assessment including self-report rating scales and blood sampling for inflammatory markers (CRP, IL-6, TNF-alpha, white blood cells).
 
Participants who also consent to the substudy will undergo an fMRI examination of the brain's reward system (MID task). Thereafter, study treatment will begin according to the protocol, with dose escalation once weekly until treatment effect, maximum dose, or intolerable side effects occur. In the event of intolerable side effects, the participant will return to the last tolerable dose. A new attempt at dose escalation may be made after seven days, up to a maximum of two attempts. If serious adverse events occur, the medication will be tapered off.
 
After ten weeks of pramipexole treatment, a final visit will be conducted including new assessment with self-rating scales and blood samples as at baseline visits (including new fMRI examination for those participating in the substudy).

Financing	
The study is financed by funds from ALF, the Söderström-Königska Foundation, SUS Donations and Foundation and the Royal Physiographic Society in Lund.

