11.2 CRITERIA FOR DISCONTINUATION OF STUDY PARTICIPATION

1. Low compliance
2. New acute suicidality
3. Deterioration by more than 25% on MADRS
4. In case of unacceptable side effects such as the development of manic state, impulse control disorder, or symptoms of heart failure
5. Pregnancy
6. The research subject may terminate his/her participation in the study at any time without incurring any consequences for his/her further treatment.

Investigators may at any time discontinue a research subject's participation in the study due to, for example, unacceptable side effects, deteriorating mental health status, or non-compliance with the procedures in the study protocol (see study adherence section 12.8).

If research subjects discontinue prematurely, a plan will be drawn up for the discontinuation of pramipexole (tapering schedule). This is done according to recommendations in FASS but can be adapted individually if needed (e.g. withdrawal side effects that lead to slower joint progression).

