The tablets are usually taken at night if the research subject does not have sleep problems. If non-tolerable side effects occur in connection with an increase in dose, the research subject is encouraged to notify this and return to the dosage that did not cause side effects. After that, wait another seven days before a new attempt at dose increase occurs. This is done on a maximum of two occasions before giving up attempts to reach a higher dosage (treatment continues with the lower dosage if possible). An exception to this strategy is if the study participant experiences side effects in the form of impulse control disorder (e.g. pathological gambling addiction or compulsive buying behavior), manic state, or symptoms of heart failure. If such a situation arise, pramipexole will be tapered off and discontinued. Study participants will be assessed with YMRS at baseline, week 2, week 4, week 6, week 8 as well as at week 10 to evaluate any manic symptoms.

The total duration of treatment is ten weeks before an evaluation of efficacy is made and a decision is made on continued treatment or discontinuation (referral is sent to PAL, which is responsible for continued treatment with pramipexole). If the research subject during the study shows a 50% decrease on MADRS or a 50% increase on DARS (=response), further dose increase is stopped, and the research subject then remains on this dose for the rest of the study. Control of *compliance* This is done by asking the research subject to bring the remaining tablets (and dosage diary) to the evaluation visits every two weeks for control counting of the number of tablets.

Pramipexole treatment must not be stopped abruptly due to the risk of dopamine *agonist withdrawal syndrome* (DAWS) with symptoms such as depression, anhedonia, apathy, anxiety, sleep disturbances, and others. The study participant is carefully informed about this. If discontinuation of the drug becomes necessary, this will be done gradually as instructed in FASS: The pramipexole dose is gradually reduced by 0.75 mg of salt per day until the daily dose is reduced to 0.75 mg of salt. The dose should then be reduced by 0.375 mg of salt per day. The patient is instructed to report any withdrawal side effects and then the dose reduction can be individualized to counter them.

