15 SECURITY MONITORING AND REPORTING

15.1 DEFINITION OF INCIDENT

Term	Definition
Incident / Adverse Event (AE)	An undesirable medical event or deterioration of existing conditions in a research subject who has received a drug, and which is not necessarily causally related to the given treatment. Examples of incident: symptoms (nausea, somnolence, development of hypertension, development of mania).
Side effect / Adverse Reaction (AR)	An adverse medical event that is judged by a medically competent to have a reasonable probability of having a causal relationship with the study drug at any dose.
Serious Incident / Serious Adverse Event (SAE)	An undesirable medical event that meets one or more of the following criteria: 1. Death. 2. Life-threatening conditions. The term "life-threatening" refers to an event in which the participant was at risk of death at the time of the event. It does not refer to an event that hypothetically would have caused death if it were more serious. 3. Requires hospital care or prolongs an already started hospital session. 4. Causes a permanent or significant disability or disability. 5. Constitutes a congenital malformation or congenital defect. 6. Other medically significant event for the research subject that requires an intervention to prevent one of the above-mentioned criteria.
Serious adverse reaction Serious Adverse Reaction (SAR)	An adverse medical event that is both serious and is judged by a medically competent person to have a reasonable probability of having a causal relationship with the study medication.
SUSAR Suspected Unexpected Serious Adverse Reaction (SUSAR)	A suspected serious side effect that is unexpected, i.e. the nature and severity of which do not correspond to the known information on the medicine as specified in the reference safety information (Investigator's Leaflet [IB]) or Summary of Product Characteristics).

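### The synopsis tapers pramipexole after any serious adverse event; sections 11.2, 13.3 and 15 contain no such rule, and the step-back default in 13.3 can direct the opposite

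*Combined protocol and SAP*

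**What the plan says.** **Synopsis (section 5, Method description).** Intolerable side effects lead to a return to the last tolerated dose, with a new attempt after seven days and at most two attempts. A separate sentence follows: "If serious adverse events occur, the medication will be tapered off".

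**Section 15.1.** An adverse event is one "which is not necessarily causally related to the given treatment". A serious adverse event is one that meets any of six criteria, one of which is "Requires hospital care or prolongs an already started hospital session". Serious adverse reactions, where a causal link is judged reasonably probable, are defined separately.

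**Section 11.2.** Item 4 on ending participation reads "In case of unacceptable side effects such as the development of manic state, impulse control disorder, or symptoms of heart failure". Other items cover low compliance, new acute suicidality, "Deterioration by more than 25% on MADRS", pregnancy and the participant's own wish. A discretionary clause begins "Investigators may at any time discontinue a research" and gives examples. Serious adverse events are not named.

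**Section 13.3.** For intolerable side effects linked to a dose increase, the participant goes back to the earlier dose, waits seven days and tries again, at most twice. Treatment then continues at the lower dose if possible. Next comes: "An exception to this strategy is if the study participant experiences side effects in the form of impulse control disorder", with manic state and heart-failure symptoms named alongside. For these, "If such a situation arise, pramipexole will be tapered off and discontinued".

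**Sections 15.5 and 15.7.2.** These cover recording, follow-up and reporting of serious events. They prescribe no action on study drug.

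**The concern.** The rule for stopping study drug after a serious event depends on which part of the protocol site staff consult. That matters for participants first. Section 8 states that no external safety committee is considered justified, so the written rule carries more weight. Tapering is not a neutral fallback either: 12.7 and 13.3 warn of withdrawal effects that include depression, apathy and, in 13.3, anhedonia.

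It also bears on interpretation. Whether high-dose pramipexole is tolerable is one of the study's questions, and the primary comparison uses DARS at week 10. The instruction followed after a serious event decides whether that participant is still on drug at week 10. For early discontinuation, 12.7 offers a visit or a telephone contact and does not specify a DARS rating.

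**Working it through.** The point is textual, so the check sets the instructions side by side for specific events. Hypotension and confusion are used as examples because 13.1 lists both as common side effects.

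| Event | Synopsis | 13.3 | 11.2 | Section 15 |
|---|---|---|---|---|
| A. Hypotension or confusion after a dose increase, leading to hospital care | Taper | Step back, wait seven days, try again | May be stopped if judged unacceptable | Report and follow |
| B. Hospital admission unrelated to study drug | Taper | Silent (not a side effect) | No specific criterion; discretion only | Report and follow |
| C. Manic state that meets no seriousness criterion | Taper sentence does not apply | Taper | Listed as a reason to end participation | Record and follow |
| D. Manic state leading to hospital care | Taper | Taper | Listed | Report and follow |
| E. New acute suicidality leading to hospital care | Taper | Silent | Listed, with a tapering plan | Report and follow |

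1. **Rows D and E agree in effect.** For several serious events that are plausible in this population, the passages lead to the same action.
2. **Row A conflicts.** Hospital care makes the event serious under 15.1, so the synopsis calls for taper. The event is also an intolerable side effect at a dose increase and lies outside the three exceptions, so the default in 13.3 calls for a lower dose and a new attempt.
3. **Row B is a gap.** The definition in 15.1 does not depend on cause, and serious reactions have their own term there. Read with its defined meaning, the synopsis sentence therefore covers an unrelated admission. The body gives no instruction for it.
4. **Row C shows a mismatch in the other direction.** Section 13.3 requires taper for an event that the synopsis sentence does not reach. Neither set of triggers contains the other.
5. **The hospital criterion can realistically be met.** The synopsis and section 11 allow recruitment from inpatient wards, so a prolonged stay is possible as well as a new admission.

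The only planning figure that depends on losses is the enrolment in 16.1. With 10 completers required and dropout at the stated limit of one-third, 10 / (1 − 1/3) = 15, which matches the plan. The taper rule is not an input to that calculation or to the 16.6-point detectable difference.

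**The case against.** The strongest reply is that the synopsis sentence is loose shorthand. It follows the same order as 13.3 (step back, wait, two attempts, then the case for taper) and sits where 13.3 places its exceptions. On that reading only a summary is imprecise. The parallel is real, but it does not remove the problem. Rows A to C show that the triggers differ in both directions, and the term used in the synopsis has a formal definition in 15.1.

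A second reply is that an investigator could satisfy all the passages by tapering, because nothing says that treatment must continue after a serious event and 11.2 lets the investigator stop at any time. This largely stands for row B, which is an omission and not a contradiction. It does not stand for row A, where the default in 13.3 directs a further attempt at escalation. Permission to stop under 11.2 does not settle a mandatory taper against a prescribed retry.

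Three stronger readings are tempting, and the documents do not support them:

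- A reader might infer that 11.2 also requires stopping only for named events. Its side-effect item is an open list, it has other criteria, and it gives the investigator discretion. Only the taper sentence in 13.3 is a closed list.
- A reader might infer that the mismatch determines who counts as a dropout. Dropout is counted in 9.3 and 16.3 but never defined. The synopsis sentence concerns tapering the drug while 11.2 concerns ending participation, and the full analysis set is primary. The missing definition is a separate gap.
- A reader might put the effect at 1/15 = 6.7% per extra stop. That is the share of any single participant and does not measure what this wording does.

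Alignment would also not remove case-by-case selection, since the discretion in 11.2 would remain.

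**Conclusion.** The point holds as an inconsistency in a safety rule. The synopsis mandates taper after any serious adverse event and no body section repeats it. For a serious side effect at a dose increase outside the three events named in 13.3, the synopsis and 13.3 point in opposite directions. For an unrelated admission, the synopsis says taper and the body states no action.

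The conclusion rests on reading the synopsis term with its definition in 15.1. Its size cannot be stated, because the documents give no serious-event rate; section 8 describes the risk of severe events as very small at the doses planned. No enrolment or power figure changes. It is worth correcting because it affects what is done to a participant and the correction is small.

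**What to change.** Reconcile the synopsis, 11.2 and 13.3 so that all three carry one rule. It should state what happens to study drug after a serious adverse event as defined in 15.1, whether relatedness to study drug matters, and how the rule sits with the step-back default and the three exceptions in 13.3. The sponsor and investigator must decide which rule applies; this review takes no position on that.

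The cost is one aligned sentence in each of the three places. If the sponsor judges the change significant under 20.1, it would also need to be submitted as an amendment. No new data collection or analysis is needed.

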6 STUDY FLOW CHART

7 BACKGROUND AND RATIONALE

Affective disorders are psychiatric syndromes whose main symptoms are changes in affectation or mood. Examples of such disorders are major depression (unipolar depression), bipolar disorder and Dysthymia. Today's treatment methods for mood disorders are often inadequate. From the start of drug treatment, it usually takes a few weeks before the treatment effect becomes noticeable, even though any side effects often occur earlier¹. In addition, a large proportion of patients do not respond at all to drug treatment despite several treatment attempts, and many of those who respond to the treatment have severe and function-limiting residual symptoms in the form of, for example, anhedonia and lack of motivation². It is estimated that up to a third of patients with depression do not reach remission despite repeated treatment attempts with different drugs³. One reason for this is that the diagnostic criteria in manuals and systems such as DSM-5 and ICD-10 do not consider the biological causes of the diseases. To better study depression and other affective disorders, psychiatric syndromes can be divided into so-called endophenotypes⁴, i.e. characteristic features (in this case, symptoms) with a clear biological correlation that can occur across the diagnostic boundaries and vary within the same diagnosis. In affective disorders, anhedonia has been shown to be such an endophenotype⁵.

Anhedonia - the inability to feel pleasure or reduced will/"drive" to seek pleasure - is associated with affective disorders, but also other psychiatric illnesses such as substance addiction and schizophrenia⁶. Anhedonia is found in 20-40% of all cases of major depression and is a risk factor for developing depression with more severe symptoms, longer disease course, treatment resistance and suffering from relapse in depression⁷. Currently, there is no effective and/or specific treatment for the symptoms of anhedonia. The onset of anhedonia is thought to be due to dysfunction in the brain's reward system⁸. An important structure in the brain's reward system is the accumbens nucleus (NAc). fMRI scans have shown an increased neural activity in NAc in healthy individuals with an expectation of receiving a reward; In patients with depression and anhedonia symptoms, the corresponding activity is reduced⁹. In NAc, there are neurons that express the dopaminergic receptor D3¹⁰. The D3 receptor is considered a potential target for the treatment of anhedonia and in animal studies antidepressant effects of D3 receptor agonists have been demonstrated¹¹. Most of today's drug treatments for depression affect dopaminergic neurotransmission, such as monoamine oxidase inhibitors (MAOIs) and bupropion, but none of these act as D3 receptor agonists.

Anhedonia and similar symptoms have also been associated with increased systemic inflammation¹². For example, depressed patients with increased levels of inflammation markers in the blood have reduced connectivity ("communication") between the reward system and other parts of the brain¹³. Several studies have also shown that inflammation affects dopamine metabolism in the brain, and patients with concomitant low-grade systemic inflammation and depression respond better to bupropion (which increases dopamine in the synapses) compared to other patients with depression without increased inflammation¹⁴. Thus, drugs that affect dopaminergic nerve transmission are likely to provide better treatment efficacy in depressed patients with signs of systemic inflammation compared to patients with depression as a whole.

Pramipexole is a selective D3 receptor agonist which is primarily used as a treatment for Parkinson's disease (PS) and Willis-Ekbom disease (*Restless Legs syndrome*). Patients with PS often suffer from depression with anhedonia symptoms and it has been suggested that pramipexole has antidepressant effects in these patients by affecting dopaminergic neurotransmission¹⁵. Pramipexole has also been investigated in a small, randomized trial in unipolar and bipolar depression¹⁶⁻¹⁸. However, the clinical

effect has been too small to be widely justify treatment with pramipexole instead of usual antidepressants that have fewer side effects. However, in these studies, relatively low doses of pramipexole (an average of 1.0 mg) have been used when treating with pramipexole between 0.375 and 4.5 mg in Parkinson's disease. *The American Journal of Psychiatry* recently published a clinical review of patients with bipolar or unipolar therapy-refractory depression treated with pramipexole as adjunctive therapy. Interestingly, 76% reported an improvement that persisted up to 16 months after the end of treatment with an average dose of 2.5 mg pramipexole¹⁹. These results are promising because the patients in the study had a high degree of therapy resistance (several had not responded to ECT, for example), but the study was uncontrolled and took place within "clinical routine". Thus, well-controlled and systematic studies are needed before pramipexole can be recommended in the clinic.

In this pilot study, we want to test the efficacy and tolerability of pramipexole in the higher dose range (> 1.5 mg, max 4.5 mg salt) in patients with depression and with significant anhedonia symptoms despite usual treatment. The results of the study will form the basis for designing a larger placebo-controlled randomized trial. We also want to test the conditions for an fMRI scan before and after treatment to be able to demonstrate "*target engagement*". The aim of this is to eventually find biomarkers that can predict the treatment response of pramipexole.

